5.0 STUDY OBJECTIVES AND ENDPOINTS

5.1 Objectives

5.1.1 Primary Objective

The primary objective of this study is to evaluate the efficacy of TAK-385 40 mg administered orally once daily for 12 weeks, compared with leuprorelin injection (once/4 weeks, 1.88 mg or 3.75 mg SC/time) in subjects with uterine fibroids.

5.1.2 Secondary Objectives

The secondary objective of this study is to evaluate the efficacy and safety of TAK-385 40 mg administered orally once daily for 24 weeks, compared with leuprorelin injection (once/4 weeks, 1.88 mg or 3.75 mg SC/time) in subjects with uterine fibroids.

5.1.3 Additional Objectives

An additional objective of this study is to evaluate the pharmacodynamic effect, which is blood concentrations of LH, FSH, E₂, and P.

5.2 Endpoints

5.2.1 Primary Endpoint

1) Efficacy:

Proportion of subjects with a total PBAC score of < 10 from Week 6 to 12

5.2.2 Secondary Endpoints

1) Efficacy:

- Proportion of subjects with a total PBAC score of < 10 (from Week 2 to 6, from Week 18 to 24, and for 6 weeks before the final dose of study drug)
- Myoma volumes (Week 2, 4, 8, 12 and 24)

Note: Only the largest myoma among those measurable at VISIT 1 will be measured throughout the study.

- Uterine volumes (Week 2, 4, 8, 12 and 24)
- Hemoglobin (HGB) (Week 4, 8, 12, 16, 20, 24 and Follow-up)
- Numerical Rating Scale (NRS) score (from Week 6 to 12, from Week 2 to 6, from Week 18 to 24, and for 6 weeks before the final dose)
- Uterine fibroid symptom and QOL (UFS-QOL) score (Week 4, 8, 12, 16, 20, 24 and Follow-up)

2) Safety:

- Adverse events (AEs), vital signs, weight, standard 12-lead electrocardiogram (ECG), clinical laboratory tests, BMD, biochemical bone metabolism markers (serum N-telopeptide [NTELOP] and bone specific alkaline phosphatase [BAP])

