6.1.1 Study Population and Design

This is a phase 3, multicenter, randomized, double-blind, parallel-group, non-inferiority study to evaluate the efficacy and safety of TAK-385 compared with leuprorelin injection (once/4 weeks, 1.88 mg or 3.75 mg SC/time) in premenopausal subjects ≥ 20 years of age with symptomatic uterine fibroids. The primary objective is to evaluate the efficacy of TAK-385 40 mg administered orally once daily for 12 weeks. The secondary objective is to evaluate the efficacy and safety of TAK-385 40 mg administered orally once daily for 24 weeks. In addition, the pharmacodynamics of continuous oral administration of TAK-385 40 mg for 24 weeks is to be assessed.

Subjects must be diagnosed to have uterine fibroids as confirmed by transvaginal ultrasound or other methods, and have symptoms of menorrhagia (the total PBAC score of ≥ 120 for the entire menstrual cycle immediately before VISIT 3). The total number of subjects to be randomized under double-blind conditions is 288 (144 subjects each for the TAK-385 40 mg group or leuprorelin group).

After signing the informed consent form, subjects will start recording in the patient diary from the day of VISIT 1. During the period between VISIT 2 and VISIT 3, in which subjects must experience 1 menstrual cycle, the baseline values for the efficacy evaluation, including PBAC scores and pain symptoms (baseline PBAC score: the total PBAC score for the entire menstrual cycle immediately before VISIT 3) will be collected. Subjects should record in the patient diary every day until the end of study drug administration. VISIT 2 should be between the first and fifth day of the first menstruation after VISIT 1. The study drug (TAK-385 placebo and leuprorelin placebo) will be administered under single-blind conditions from the day of VISIT 2 to the day before VISIT 3. VISIT 3 should be between the first and fifth day of the second menstruation after VISIT 1. From VISIT 3 to 10, subjects will receive study drug (TAK-385 and leuprorelin placebo, or TAK-385 placebo and leuprorelin) in a double blind manner. Subjects should try to visit the study site during the morning in a fasted state and before taking the TAK-385 tablet.

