7.1.3 Inclusion Criteria for Entering the Treatment (at VISIT 3)

10. The subject has 1 or more measurable noncalcified myomas, with a longest diameter of ≥ 3 cm confirmed by transvaginal ultrasound (the same myoma should be measured as in Inclusion criterion #6).
11. The subject has a diagnosis of menorrhagia with a total PBAC score of ≥ 120 in 1 menstrual cycle just before VISIT 3.
12. The subject has experienced regular menstrual cycles (25 to 38 days) after VISIT 1 that should include menstrual bleeding of at least 3 consecutive days (at least 3 regular menstruation cycles to be confirmed by Inclusion criteria #7, #9 and #12).

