9.3.2 Treatment

9.3.2.1 VISIT 3 (Day 1)

The subject visits the study site between the first and fifth day of the second menstruation after VISIT 1, without taking the TAK-385 tablet for the Run-in in the morning.

Subjects who satisfy all of the inclusion criteria and do not meet the exclusion criteria are randomized in the manner described in Section 8.2. Study drugs for the Treatment are started on the day of VISIT 3. If a dose is missed before breakfast, subjects may take the TAK-385 tablet before lunch on the same day. If a dose is missed before breakfast and lunch, subjects may take the TAK-385 tablet before dinner on the same day. The procedure for documenting the records of subjects withdrawn before randomization is provided in Section 9.1.14. Subjects are randomized after eligibility assessment on Day 1 (VISIT 3).

The following procedures should be performed at VISIT 3:

- Inclusion and exclusion criteria
- Pregnancy test (urine)

- Physical examination
- Vital signs and weight
- Patient diary (collected and distributed)
- Transvaginal ultrasound (see Section 9.1.17. If it cannot be performed at VISIT 3, it is performed between VISIT 2 and VISIT 3 [but should be done at nearest point to VISIT 3])
- BMD (perform between VISIT 2 and VISIT 3 so that the results can be reviewed at VISIT 3)
- UFS-QOL
- WPAI:GH
- Anemia-related measurements
- Clinical laboratory tests
- Pharmacodynamic measurements
- Standard 12-lead ECG
- AE
- Concomitant medications
- Dispensing of study drugs for the Treatment
- Compliance of study drug administration
- PGx sample collection (perform only in subjects who consent to participate in PGx research [see Section 9.1.12])

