7.1.1 Study Definitions

Duration of exposure to double-blind study drug (days) :

Date of last dose of double-blind study drug - date of first dose of double-blind study drug +
1

Double-blind study drug compliance (%) :

Number of TAK-385 blinded drugs taken/duration of exposure to TAK-385 blinded drug *
100 (rounded to 1 decimal places)

Disease duration (years):

((year of informed consent*12 + month of informed consent) -(year of first defined diagnosis of uterine fibroids*12 + month of first defined diagnosis of uterine fibroids))/12 (rounded to 1 decimal places)

Maximum drug holidays (days):

Maximum number of consecutive days on which the subject does not take the TAK-385 blinded drug for the treatment period

Total PBAC score from Week 6 to 12

Total PBAC score from Day 43 to earlier of Day 84 or Follow-up Day 3.

Similarly, Total PBAC score from Week 2 to 6 and from Week 18 to 24 will be defined as

those from Day 15 to earlier of Day 42 or Follow-up Day 3 and from Day 127 to earlier of Day 168 or Follow-up Day 3, respectively.

Total PBAC score for 6 weeks before the final dose of study drug

Total PBAC score for the last 42 days of the treatment

NRS score from Week 6 to 12

Average NRS score from Day 43 to earlier of Day 84 or Follow-up Day 3.

Similarly, NRS score from Week 2 to 6 and from Week 18 to 24 will be defined as average NRS score from Day 15 to earlier of Day 42 or Follow-up Day 3 and from Day 127 to earlier of Day 168 or Follow-up Day 3, respectively.

NRS score for 6 weeks before the final dose

Average NRS score for the last 42 days of the treatment

Total PBAC at baseline

Total PBAC score from first day of menstrual period confirmed at Visit 2 to a day prior to menstrual period confirmed at Visit 3

NRS score at baseline

Average NRS score from first day of menstrual period confirmed at Visit 2 to a day prior to menstrual period confirmed at Visit 3

Use of analgesic medications during the treatment from Week 6 to 12

((number of days with analgesic medications use between Day 43 and earlier of Day 84 or Follow-up Day 3)/(number of days with available data between Day 43 and earlier of Day 84 or Follow-up Day 3))*100 (rounded to 1 decimal places)

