7.1.2 Definition of Study Days

When calculating Study Day relative to a reference date (ie, date of first dose of double-blind study drug [Day 1]) , if the date of the observation is on the same date or after the reference date, it will be calculated as: date of observation - reference date + 1; otherwise, it will be calculated as: date of observation - reference date. Hence, reference day is always Day 1 and there is no Day 0.

When calculating Follow-up Day relative to a reference date (ie, date of last dose of double-blind study drug [Follow-up Day 0]) , it will be calculated as: date of observation - reference date. Hence, reference day is always Follow-up Day 0.

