7.8.2 Secondary Efficacy Endpoint(s)

7.8.2.1 PBAC Score

Analysis Set: Full Analysis Set

Analysis

Variable(s): Proportion of subjects with a total PBAC score of < 10 from Week 2 to 6
Proportion of subjects with a total PBAC score of < 10 from Week 18 to 24
Proportion of subjects with a total PBAC score of < 10 for 6 weeks before the final dose of study drug

Analytical

Method(s): For each variable, frequency will be summarized by treatment group. The point estimate and 2-sided 95% confidence interval of the difference in the percentage will be calculated between TAK-385 40 mg group and leuprorelin group, using FM method with the non-inferiority margin of -15%. The confidence interval will be presented in a descriptive manner and not for the purpose of statistical inference.

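### The final-6-weeks windows have no earliest start day, so for women who stop by about Day 42 to 48 they can take in the menstruation already under way at the first dose

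*Protocol*

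**What the plan says.** Protocol 5.2.2 lists the proportion with total PBAC below 10 over three periods, the last being "and for 6 weeks before the final dose of study drug". SAP 7.1.1 turns this into "Total PBAC score for the last 42 days of the treatment". It treats pain the same way, "Average NRS score for the last 42 days of the treatment", and analgesic use is the percentage of days with use over the same period. SAP 7.8.2.1 analyses "Proportion of subjects with a total PBAC score of < 10 for 6 weeks before the final dose of study drug", and SAP 7.8.3.4 repeats the period for PBAC = 0. None of these definitions gives an earliest start day or a rule for fewer than 42 treated days.

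On the start of treatment, Protocol 6.1.1 says "VISIT 3 should be between the first and fifth day of the second menstruation after VISIT 1" and Protocol 9.3.2.1 says "Study drugs for the Treatment are started on the day of VISIT 3". SAP 7.1.2 makes the first double-blind dose Day 1. The baseline PBAC in SAP 7.1.1 stops before the VISIT 3 menstruation, so that bleed falls in the treatment period.

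The fixed windows in SAP 7.1.1 start on Day 15 (Week 2 to 6), Day 43 (Week 6 to 12) and Day 127 (Week 18 to 24). The full analysis set needs only one dose (Protocol 13.1.1). SAP 7.2 leaves the analysis sets to the Handling Rules for Analysis Data, which are not among the documents.

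**The concern.** Entry requires a cycle PBAC of at least 120, twelve times the response cut-off, and drug starts within the first five days of a menstruation. The fixed windows step over that bleed. The final-6-weeks window does so only if treatment lasts long enough. In an early stopper, bleeding and pain from the menstruation already running at the first dose would be counted as end-of-treatment outcome.

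One diary could then give opposite answers. A woman with last dose on Day 35 is scored over Day 15 to 38 for Week 2 to 6 (Follow-up Day 3 is Day 38), but over Day 1 to 35 for the final 6 weeks.

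The error need not be equal between arms. Protocol 4.1 says that GnRH agonists take about 3 to 4 weeks to begin working and that TAK-385 acts faster. Among early stoppers, more women on TAK-385 than on leuprorelin could be suppressed yet scored as failures.

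**Working it through.** **Plan's own figures.** The plan gives no figure for this endpoint. Its sample size reproduces: (1.960 + 1.282)² × 2 × 0.836 × 0.164 / 0.15² = 128.05, so 129 per group, and 129 / 0.9 = 143.3, so 144. Neither is in question here.

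**Window.** Let L be the day of the last dose. On-treatment days only gives Day max(1, L − 41) to Day L. Cutting at Day 1 is my reading of the SAP wording.
- L = 30: Day 1 to 30
- L = 42: Day 1 to 42
- L = 45: Day 4 to 45
- L = 48: Day 7 to 48
- L = 56: Day 15 to 56

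**Overlap with the VISIT 3 bleed.** Let VISIT 3 fall on menstrual day v (1 to 5) and bleeding last m days. The criteria give only a minimum, "menstrual bleeding of at least 3 consecutive days"; I assume m = 3 to 8. Bleeding ends on Day b = m − v + 1, so the window holds a bleeding day when b ≥ 1 and L ≤ 41 + b. The latest such L is:
- m = 3: Day 44, 43, 42 for v = 1 to 3, and none for v = 4 or 5, when bleeding is already over
- m = 5: Day 46, 45, 44, 43, 42 for v = 1 to 5
- m = 7: Day 48, 47, 46, 45, 44 for v = 1 to 5
- m = 8, v = 1: Day 49

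**Points carried in.** Protocol 9.1.16 gives 1, 5 or 20 points per pad, so one saturated pad or two moderately stained pads reach 10. Assume that the VISIT 3 bleed also totals 120, lasts 5 days and is not cut short by drug. With last dose on Day 42, the points from this bleed alone are:

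| Daily pattern | v=1 | v=2 | v=3 | v=4 | v=5 |
|---|---|---|---|---|---|
| Flat | 120 | 96 | 72 | 48 | 24 |
| Linear fall | 120 | 80 | 48 | 24 | 8 |
| Halving | 120 | 58 | 27 | 12 | 4 |

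Only the two tapering cases at v = 5 stay below 10. For PBAC = 0, a single lightly stained pad is enough to fail. Across m = 3, 5 and 7 at a total of 120, the latest last-dose day that still brings in 10 points is, where any day does, Day 42 to 48 (flat), 42 to 47 (linear) or 42 to 45 (halving).

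**Size.** The documents give no stopping times. Assume 5% to 10% of each arm stop by Day 84, evenly over time. Only stops on Day 15 to 47 can be suppressed after Day 14 and still be failed by the early bleed. Their share is 5% to 10% × 33/84 = 2.0% to 3.9%, or 2.8 to 5.7 of 144. The shift in the difference is that share × (suppressed share on TAK-385 − suppressed share on leuprorelin):
- 50% against 40%, 5% stopping: 0.05 × 33/84 × 0.1 = 0.2 points
- 80% against 0%, 10% stopping: 0.10 × 33/84 × 0.8 = 3.1 points

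For scale, the 95% half-width at 83.6% is 1.96 × √(2 × 0.836 × 0.164 / 144) = 8.6 points.

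**The case against.** The SAP does not say how to score fewer than 42 treated days. Cutting at Day 1 is an inference, and the Handling Rules may set a minimum exposure or leave such women unscored. That stands, and the point is limited to the text available. A reader might go further and take the protocol's wording to reach back into the placebo run-in; the SAP's restriction to days of the treatment does not support that.

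A reader might also infer that every woman who stops by Day 48 fails by construction. The table shows otherwise, and after Day 42 the result depends on bleed length, VISIT 3 day and daily pattern. Nor does it carry over to NRS and analgesic use, which are an average and a percentage with no response cut.

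It can fairly be said that a woman who stops before six weeks has not shown a six-week response, so failing her is prudent. That is a defensible rule, but it is not the one written: the outcome turns on how much of the entry bleed remained. The documents also nowhere say that this endpoint exists to give every treated woman a result.

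Finally, SAP 7.8.2.1 makes the interval descriptive, and the likely direction is against TAK-385. Both are correct and keep the weight low. Even the direction is not certain: women who leave for lack of efficacy or low hemoglobin (Protocol 7.5) may not be suppressed at all.

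**Conclusion.** The gap in the definition is real and minor. As SAP 7.1.1 reads, a last dose by Day 42 brings the remainder of the entry menstruation into the final-6-weeks result, and a last dose on about Day 43 to 48 may bring in part of it. Most of these women would miss PBAC < 10, and nearly all would miss PBAC = 0, for a reason unrelated to the drug.

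On the assumptions above, the between-arm difference moves by 0.2 to about 3 points. The top needs 10% stopping and an extreme 80% against 0% suppression. A reader might reach 4.5 points by applying suppression to all stops by Day 47 (0.10 × 47/84 × 0.8), but women who stop by Day 14 have no treated day after Day 14 on which to be suppressed. With no stops before about Day 49 the effect is zero.

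The primary endpoint is not affected, because its window starts on Day 43.

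**What to change.** In SAP 7.1.1, define the final-6-weeks window as Day max(15, last-dose day − 41) to the last-dose day for PBAC < 10, PBAC = 0, NRS and analgesic use, scored on available days as the fixed windows are. Day 15 is the start the SAP already uses for Week 2 to 6. Nothing changes for a last dose on Day 56 or later.

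Report by arm how many women have a window shorter than 42 days (last dose on Day 15 to 55) or none (last dose before Day 15). Add one sensitivity row that counts them all as non-responders for the two PBAC proportions. If the Handling Rules already set a minimum exposure, refer to it in SAP 7.1.1.

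I would not add a minimum such as 28 days. With a Day 15 floor it would leave unscored every woman whose last dose is before Day 42, which is an exclusion after randomization.

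The cost is one sentence, one count and one table row before unblinding. The downside is that a short window makes PBAC < 10 easier to meet and may not span the 38-day cycle that Protocol 6.2.3.1 used to choose six weeks. The sensitivity row shows how much that matters.

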5.2.3 Additional Endpoints

1) Efficacy:

- Hematocrit (HCT), serum iron (Fe), and serum ferritin (Week 4, 8, 12, 16, 20, 24 and Follow-up)
- Use of analgesic medications during the Treatment (from Week 6 to 12, from Week 2 to 6, from Week 18 to 24, and for 6 weeks before the final dose)
- Work Productivity and Activity Impairment Questionnaire:General Health (WPAI:GH) (Week 2, 4, 8, 12 and 24)

2) Safety:

- Period from the last dose of study drug to return of menstrual cycles

3) Pharmacodynamic effects:

- LH, FSH, E₂ and P (Week 2, 4, 8, 12, 16, 20, 24 and Follow-up)

6.0 STUDY DESIGN AND DESCRIPTION

6.1 Study Design

An overview of the study design is shown in [Figure 6.a](#). See [Appendix A](#) for details of the schedule of tests, observations, and evaluations.

6.1.1 Study Population and Design

This is a phase 3, multicenter, randomized, double-blind, parallel-group, non-inferiority study to evaluate the efficacy and safety of TAK-385 compared with leuprorelin injection (once/4 weeks, 1.88 mg or 3.75 mg SC/time) in premenopausal subjects ≥ 20 years of age with symptomatic uterine fibroids. The primary objective is to evaluate the efficacy of TAK-385 40 mg administered orally once daily for 12 weeks. The secondary objective is to evaluate the efficacy and safety of TAK-385 40 mg administered orally once daily for 24 weeks. In addition, the pharmacodynamics of continuous oral administration of TAK-385 40 mg for 24 weeks is to be assessed.

Subjects must be diagnosed to have uterine fibroids as confirmed by transvaginal ultrasound or other methods, and have symptoms of menorrhagia (the total PBAC score of ≥ 120 for the entire menstrual cycle immediately before VISIT 3). The total number of subjects to be randomized under double-blind conditions is 288 (144 subjects each for the TAK-385 40 mg group or leuprorelin group).

After signing the informed consent form, subjects will start recording in the patient diary from the day of VISIT 1. During the period between VISIT 2 and VISIT 3, in which subjects must experience 1 menstrual cycle, the baseline values for the efficacy evaluation, including PBAC scores and pain symptoms (baseline PBAC score: the total PBAC score for the entire menstrual cycle immediately before VISIT 3) will be collected. Subjects should record in the patient diary every day until the end of study drug administration. VISIT 2 should be between the first and fifth day of the first menstruation after VISIT 1. The study drug (TAK-385 placebo and leuprorelin placebo) will be administered under single-blind conditions from the day of VISIT 2 to the day before VISIT 3. VISIT 3 should be between the first and fifth day of the second menstruation after VISIT 1. From VISIT 3 to 10, subjects will receive study drug (TAK-385 and leuprorelin placebo, or TAK-385 placebo and leuprorelin) in a double blind manner. Subjects should try to visit the study site during the morning in a fasted state and before taking the TAK-385 tablet.

The study consists of Screening of approximately 1 to 6 weeks, a Run-in period of 3 to 6 weeks, a Treatment period of 24 weeks, and a Follow-up period of 4 weeks. The total period of study participation is approximately 32 to 40 weeks. If the recovery of the first post-treatment menstruation is not observed by the visit at the end of the Follow-up (VISIT 11), the subject will undergo further follow-up using possible means such as by telephone interview, until the recovery of the first post-treatment menstruation is observed. During the course of this study, subjects will visit the study site to undergo the designated examinations and evaluations at each visit, every 2 weeks for a month after the initiation of study drug administration (VISIT 3) under double-blind conditions, and monthly thereafter.

CONFIDENTIAL

6.1.2 Dose Level and Regimen

At VISIT 3, subjects will be randomized in a 1:1 ratio to either the TAK-385 40 mg group or leuprorelin group. Study drug (TAK-385 40 mg + leuprorelin placebo or TAK-385 placebo + leuprorelin) will be administered in a double-dummy method from the day of VISIT 3 to the day before VISIT 10 (or until early termination) under double-blind conditions.

The investigator or subinvestigator will decide the dosage of leuprorelin at VISIT 2 in accordance with the approved dosage and administration, considering the body weight and symptoms of the individual subject. Leuprorelin (or leuprorelin placebo) should be administered SC (injection) once every 4 weeks using the same dose throughout the Run-in and Treatment.

TAK-385 (or TAK-385 placebo) will be administered daily as a single oral dose before breakfast.

[figure not shown]

Figure 6.a Schematic of Study Design

6.2 Justification for Study Design, Dose, and Endpoints

6.2.1 Justification for Study Population and Design

Menorrhagia is the most frequent symptom seen in patients with uterine fibroids. Patients with menorrhagia have to frequently replace sanitary products. In addition, prolonged menorrhagia can induce iron-deficiency anemia. Therefore, menorrhagia is the main cause of QOL deterioration¹. Surgery is performed for radical treatment of uterine fibroids. Drug therapy is used before surgery to alleviate anemia and to reduce the size of myoma^{2,3}. TAK-385 is thought to overcome the shortcomings of GnRH agonists commonly used in preoperative therapy. In this study, the improvement in the bleeding profile is examined for evaluation of improvement of QOL and efficacy of TAK-385 in patients with uterine fibroids.

The study is designed as a double-blind, parallel-group study to demonstrate the non-inferiority of TAK-385 compared with leuprorelin which is commonly used for the treatment of uterine fibroids. Since the period of general presurgical treatment for uterine fibroids is 3 months, which is stated to be a period for decreasing the size of myoma and improving anemia in some reports³, the evaluation period of drug efficacy for the primary endpoint is to be set as 3 months. However, since medication for more than 3 months may sometimes be needed as a maintenance therapy, evaluation of drug efficacy and safety for up to 6 months are to be set as secondary endpoints. In benign indications GnRH agonist administration exceeding more than 6 months is generally not permitted because it may cause BMD loss resulting from a decrease in estrogen level.

The Treatment for this study is set at 6 months to evaluate the safety of TAK-385 and the potential effect of TAK-385 on BMD compared to GnRH agonists in subjects with uterine fibroids and menorrhagia. A single-blind treatment period (with placebo) is also included to investigate if there is any potential placebo effect on baseline blood loss and pain assessment. In addition, the Follow-up is included for safety assessment, including assessment of the recovery of menstruation after discontinuation of active treatment.

